
 To assess the PD effect of efgartigimod 	
 Values, changes from baseline, and percent reduction from baseline in total IgG levels in serum over the 48-week treatment period Values, changes from baseline, and percent reduction from baseline in autoantibodies in serum over the 48-week treatment period: 
 Anti-Ro/SS A Anti-La/SS B

 To assess the exposure to efgartigimod 	
 Efgartigimod serum concentrations over the 48-week treatment period

 To assess the immunogenicity of efgartigimod 	
 Incidence and prevalence of ADA against efgartigimod over the 48-week treatment period
Exploratory	

 To explore the effect of efgartigimod on additional clinical pSS measures 	
 Proportion of responders on 2 of 4 items of the adjusted CRESS (without serology item) at weeks 24 and 48 when compared to baseline Change from baseline in activity of individual ESSDAI domains at weeks 24 and 48

 To explore the effect of efgartigimod on glandular measures 	
 Change from baseline in: 
 SWSF rate at weeks 24 and 48 UWSF rate at weeks 24 and 48 Hocevar score at weeks 24 and 48 Schirmer's test at weeks 24 and 48 OSS at weeks 24 and 48 Response in salivary gland as defined in CRESS at weeks 24 and 48 when compared to baseline Response in tear gland as defined in CRESS at weeks 24 and 48 when compared to baseline

 To explore the effect of efgartigimod on patient-reported outcomes 	
 Change from baseline in: 
 Total MFI score at weeks 24 and 48 Physical component and mental component scores of SF-36 at weeks 24 and 48 PGA at weeks 24 and 48 Individual ESSPRI scores at weeks 24 and 48 EQ-5D-5L utilities and VAS scores at weeks 24 and 48 PASS at weeks 24 and 48 when compared to baseline

Objectives	Endpoints

 • CCI [REDACTED] 	
 • CCI [REDACTED] • Values, changes from baseline, and percent reduction from baseline in RF in serum over the 48-week treatment period

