15. IMMUNOGENICITY ANALYSIS

Incidence and prevalence of ADAs against efgartigimod will be assessed in the SAF. ADAs to efgartigimod is measured at the time points specified in the schedule of activities of protocol, primarily at baseline, week 2, 4, 8, 12, 16, 24, 36, 48 and SFV.

Immunogenicity samples are analyzed in a 3-tiered approach:

- All samples are evaluated in the ADA screening assay and are scored ADA screening positive (tier 1) or negative.
- If a sample is scored positive in the ADA screening assay, it is further evaluated in the confirmatory assay (tier 2) and is scored confirmed positive (positive immuno-depletion) or confirmed negative (negative immuno-depletion).
- If a sample is scored as confirmed positive, the samples are further characterized in the ADA titration assay (to determine titer).

[figure not shown]
If available, a titer result will be reported for the ADA confirmed positive samples. However, a titer result is not

[figure not shown]
always available:

- If the ADA confirmed positive sample could not be run in the titration assay (e.g., due to insufficient sample volume/quality to perform the titer analysis), the result will be described as “positive immuno-depletion”, and the sample should be considered ADA positive.
 - If a sample is negative in the titration assay, it will be reported as “negative titer”, but it should be considered ADA positive because it was confirmed positive in the second tier.
 - If a sample could not be analyzed or reported as “positive screen”, the ADA sample status is ADA unevaluable.
- An overview of this 3-tiered approach and all possible ADA sample results that will be reported by the laboratory is given below. From these reported ADA sample results, a final ADA sample status must be derived during the statistical analysis, as presented in the final column (“Final ADA Outcome”):

Figure 2: ADA Sample Status

Copyright © 2009, 2010, 2012, 2016, 2018, 2019, 2021, 2024 IQVIA. All rights reserved. The contents of this document are confidential and proprietary to IQVIA Holdings Inc. and its subsidiaries. Unauthorized use, disclosure or reproduction is strictly prohibited.

^a “Positive titer” is reported if it was not possible to retrieve a numerical value.

Participant Classification for ADA Against Efgartigimod

Table G below gives an overview of how the ADA participant classification will be derived, starting from the participant baseline ADA sample status.

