Table H: Participant Classification for ADA Against Efgartigimod

Participant ADA classification	Highest ^a postbaseline sample status				
	ADA negative	ADA positive (missing titer ^b)	ADA positive (negative titer ^c or numerical titer value)		ADA unevaluable
Baseline ADA sample status					
ADA negative	ADA negative	Treatment-induced ADA	Treatment-induced ADA		ADA unevaluable
ADA positive (missing titer^b)	Treatment-unaaffected ADA	ADA unevaluable	ADA unevaluable		ADA unevaluable
ADA positive (negative titer^c or numerical titer value)	Treatment-unaaffected ADA	ADA unevaluable	Titer <4x baseline titer: Treatment-unaaffected ADA	Titer ≥4x baseline titer: Treatment-boosted ADA	ADA unevaluable
ADA unevaluable	ADA unevaluable	ADA unevaluable	ADA unevaluable		ADA unevaluable

^a Highest sample status, with order (from low to high): ADA unevaluable, ADA negative, ADA positive (“positive immuno-depletion” or “positive titer”), ADA positive with titer <1 (“negative titer”), ADA positive with titer ≥1 (numerical value selecting the sample with highest titer).

^b Samples with missing titer will have a reported ADA result of “positive immuno-depletion” or “positive titer”.

^c Results reported as “negative titer”, i.e. titer value <1 will be set to a value of 1.

The following definitions will be used in the summary tables:

- ADA evaluable participant = participant classified in any of following categories: ADA negative, treatment-

unaffected ADA, treatment-induced ADA, or treatment-boosted ADA. The first 2 categories are classified as “ADA negative”, and the latter 2 are classified as “ADA positive”.

- ADA incidence = percentage of participants with treatment-induced or treatment-boosted ADA (denominator: number of evaluable participants).
- ADA prevalence = percentage of participants with treatment-unaffected ADA, treatment-induced ADA, or treatment-boosted ADA (denominator: number of evaluable participants).
- ADA unevaluable participant = participant classified as ADA unevaluable or with missing baseline ADA sample or without postbaseline ADA samples (in case no ADA data are available at all, the participant cannot be classified)

Note: A 4-fold difference in titer values is considered significant if a 2-fold serial dilution is applied (= 2 times the dilution factor).

Frequency tabulations (number and percentages) will be provided with ADA negative/positive/unevaluable samples per visit.

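### ADA prevalence uses only participants evaluable under a classification built for induced or boosted ADA, so some participants with confirmed-positive samples drop out of it

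*SAP*

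**What the plan says.** Protocol section 3 lists as a secondary endpoint: "Incidence and prevalence of ADA against efgartigimod over the 48-week treatment period".

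SAP section 15 first classifies samples. If a tier-2 confirmed positive could not be titrated, "the sample should be considered ADA positive". If its titration result was negative, "it should be considered ADA positive because it was confirmed positive in the second tier".

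Participants are then classified by Table H, which crosses baseline sample status with the highest postbaseline status. Footnote a ranks the statuses from unevaluable (lowest), through negative, untitrated positive and negative titer, to numerical titer (highest). On untitrated samples, footnote b begins "Samples with missing titer will have a reported ADA result of" and goes on to name two positive results, so these are confirmed positives.

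Two percentages follow. The rule for prevalence is "ADA prevalence = percentage of participants with treatment-unaffected ADA, treatment-induced ADA, or treatment-boosted ADA (denominator: number of evaluable participants". Incidence leaves out the unaffected category and is otherwise built the same way: "ADA incidence = percentage of participants with treatment-induced or treatment-boosted ADA (denominator: number of evaluable participants".

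Both use the same denominator. Participants outside it are defined by: "ADA unevaluable participant = participant classified as ADA unevaluable or with missing baseline ADA sample or without postbaseline ADA samples".

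**The concern.** Incidence asks whether ADA arose on treatment or rose at least 4-fold in titer. A participant with no usable baseline, or with no titers to compare, cannot answer that, and excluding them is reasonable. Prevalence asks only whether the participant has ADA. It adds unaffected and boosted ADA together, so the distinction that the titer resolves cancels out. Applying the incidence exclusion to prevalence removes people whose ADA status is already known to be positive.

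The row of Table H for a positive baseline with no titer shows this most clearly. If the highest later status is negative, the participant is treatment-unaffected and counts as prevalent. If a later sample is positive, even with a numerical titer, the participant is unevaluable and disappears from the percentage. More evidence of ADA removes the participant from ADA prevalence, and the SAP gives no reason for this.

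At stake is the accuracy of one stated secondary endpoint. The output could also look inconsistent. Three participants with untitrated positive baselines who all stay positive would appear as three baseline-positive samples and add nothing to the prevalence in the same table.

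**Working it through.** The plan states no ADA rate or missing-titer rate, so there is no figure of its own to reproduce.

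**Step 1: Table H.** Rows are baseline status; columns are highest postbaseline status.

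| Baseline | Negative | Positive, no titer | Positive, titer result | Unevaluable |
|---|---|---|---|---|
| Negative | negative | induced | induced | unevaluable |
| Positive, no titer | unaffected | **unevaluable** | **unevaluable** | **unevaluable** |
| Positive, titer result | unaffected | **unevaluable** | unaffected or boosted | **unevaluable** |
| Unevaluable | unevaluable | **unevaluable** | **unevaluable** | unevaluable |

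Of 16 cells, 2 + 4 + 4 + 2 = 12 contain a confirmed positive. Of these, 3 + 2 + 2 = 7 (bold) are unevaluable. The other 3 unevaluable cells contain none. The text also removes participants with a missing baseline or no postbaseline sample, whatever their other samples show.

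**Step 2: direction.** Let E be evaluable participants, x the positives counted, and k the confirmed positives dropped. The SAP reports x/E; restoring the k gives (x + k)/(E + k).

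(x + k)/(E + k) − x/E = k(E − x) / [E(E + k)]

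This is never negative, and is positive whenever k > 0 and x < E. Taken alone, this exclusion can only lower prevalence.

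**Step 3: size.** N = 30 is the approximate maximum in SAP section 3.2. The number with any confirmed positive (m) and k are assumptions. The SAP rule gives (m − k)/(30 − k).

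| m (true prevalence) | k = 1 | k = 2 | k = 3 |
|---|---|---|---|
| 3 (10.0%) | 2/29 = 6.9% | 1/28 = 3.6% | 0/27 = 0.0% |
| 6 (20.0%) | 5/29 = 17.2% | 4/28 = 14.3% | 3/27 = 11.1% |
| 9 (30.0%) | 8/29 = 27.6% | 7/28 = 25.0% | 6/27 = 22.2% |

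Each further exclusion costs between 2.4 points (30.0% to 27.6%) and 3.6 points (3.6% to 0.0%). With k = 0 nothing changes.

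SAP section 7.2 also asks for summaries by parent-study treatment, where one participant weighs more. Assuming 30 participants split 20 to 10 after the parent study's 2:1 allocation: in the group of 20 with 5 positives and 1 dropped, 4/19 = 21.1% against 25.0%; in the group of 10 with 2 positives and 1 dropped, 1/9 = 11.1% against 20.0%.

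**Step 4: opposing effect.** Let u be unevaluable participants with no confirmed positive, assumed truly negative. The SAP rule then gives (m − k)/(30 − k − u).
- m = 6, k = 0, u = 2: 6/28 = 21.4% against 20.0%.
- m = 6, k = 1, u = 2: 5/27 = 18.5% against 20.0%.

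The result is below m/30 only if u < k(30 − m)/m. For m = 6 and k = 1 the limit is 24/6 = 4, and at u = 4 the two agree (5/25 = 20.0%). For k = 1 the limit is 27/3 = 9 at m = 3 and 21/9 = 2.3 at m = 9.

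**The case against.** A reader might infer from the count of 7 in 12 that most participants with confirmed ADA are lost. The documents do not support that: it counts table cells, not people, and most of those cells need unusual data.
- The two cells with a positive baseline and an unevaluable later status require every available postbaseline sample to be unevaluable, because that status ranks lowest. Nine are scheduled (weeks 2, 4, 8, 12, 16, 24, 36, 48 and the safety follow-up visit).
- The three cells with an untitrated later positive apply only if no postbaseline positive has any titer result.
- Two cells, one of them also in the previous group, need an unevaluable baseline. SAP section 6.2 takes the last non-missing parent-study value, which makes a wholly missing baseline unlikely. Whether it also passes over an unevaluable sample is not stated.

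This narrows the point mainly to one case, an untitrated positive baseline followed by a titrated positive. That case is realistic: many participants enter already exposed after 2:1 allocation to efgartigimod, and SAP section 15 itself notes that a titer may not be available.

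A reader might also infer that reported prevalence will be too low. Step 4 shows why that does not follow. A third tempting reading is that section 15 contradicts itself by calling a sample positive and its donor unevaluable. The positive rule concerns samples, and the per-visit sample table can follow it. Participant classification is a separate, explicit step.

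Finally, the study is descriptive, with no hypothesis test, and no decision rule in the documents rests on ADA prevalence. Unevaluable participants and baseline sample status are tabulated alongside it, and all ADA data are listed, so a careful reader could rebuild the figure. That limits the harm, but the reported percentage would still omit known positives.

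**Conclusion.** The point holds in a limited form. The prevalence rule borrows an evaluability condition that prevalence does not need, and it removes some participants with confirmed-positive samples while keeping others with weaker evidence of ADA. Each removal lowers prevalence by 2.4 to 3.6 percentage points, assuming 30 participants, 3 to 9 of them with any confirmed positive, and up to 3 dropped.

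How many will be dropped cannot be derived from the documents; it may be none. The net direction is also open. The definition is worth correcting because it governs a stated secondary endpoint and is cheap to change, but the consequence for the trial is small.

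**What to change.** Leave Table H and the incidence definition unchanged. Replace the prevalence definition with, for example:

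> ADA prevalence is the percentage of participants with at least one tier-2 confirmed-positive sample, at baseline or postbaseline and with or without a titer, among participants with at least one postbaseline sample of evaluable status. Participants with no such postbaseline sample are shown on a separate line by baseline sample status.

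Requiring a postbaseline result matters. A denominator of anyone with at least one evaluable sample would count a participant with only a negative baseline as ADA-free over 48 weeks.

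Under this rule, five of the seven cells return to the percentage, as do participants with a missing baseline and a later positive. The two cells with a positive baseline and nothing evaluable afterwards go on the separate line, as does a positive baseline with no later sample.

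The cost is one sentence and one derived flag. Incidence and prevalence will have different denominators, which needs a footnote. Prevalence may move in either direction, because participants with an unevaluable or missing baseline and only negative later samples now enter the denominator as negative.

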17. SAFETY OUTCOMES

17.1. Primary Safety Outcomes

To assess the long-term safety and tolerability of efgartigimod in participants, the below safety endpoints are considered within the primary objectives.

- Incidence and severity of TEAEs
- Incidence and severity of AESIs
- Incidence and severity of SAEs
- changes in clinical laboratory safety results
- vital signs, and
- electrocardiogram (ECG) results

These endpoints will be assessed and reported based on the SAF.

17.1.1. Adverse Events

AEs and SAEs will be collected as defined in the [Section 10.3](#) of the protocol. Also, the AEs listed in previous study of ARGX-113-2106 which are “Ongoing” will be included for OLE study. AEs will be coded using latest version of Medical Dictionary for Regulatory Activities (MedDRA) central coding dictionary. AEs will be graded using the National Cancer Institute (NCI) Common Terminology Criteria for Adverse Events (CTCAE) version 5.0. For each AE, start and stop date/times are collected as well as severity, a seriousness flag, treatment-relatedness, relatedness to procedures, action taken towards the study drug and outcome.

Treatment-emergent adverse events (TEAEs) are defined as AEs with onset on or after the first administration of

Copyright © 2009, 2010, 2012, 2016, 2018, 2019, 2021, 2024 IQVIA. All rights reserved. The contents of this document are confidential and proprietary to IQVIA Holdings Inc. and its subsidiaries. Unauthorized use, disclosure or reproduction is strictly prohibited.

IMP up to and including 60 days after the last IMP administration before the event (refer to schematic).

D1: IMP start	D40: Start IMP interruption		D120: IMP restart	D160: Start IMP disc		D240: Study disc
IMP			IMP			
TE: D1-D40	TE: D40+60 days	Non-TE: D101-119	TE:D120-D160	TE: D160+60 days	Non-TE: >D220	

AEs will be considered treatment-emergent based on their start date/time. If the AE start date/time is incomplete or missing, the AE will be considered treatment-emergent unless the available part of the AE start or stop date/time provide evidence that the event did not occur within 60 days from last IMP administration before the event.

AE onset and duration will be calculated as follows when start and stop dates are fully known:

- AE onset day (versus first administration)
 - AE start date \geq date of first administration: AE start date – date of first administration + 1 day.
 - AE start date < date of first administration: AE start date – date of first administration.
- AE duration (days) =
 - AE end date – AE start date + 1 day.
 - study discontinuation date – AE start date + 1 day (when the AE start date is fully known but the AE is not resolved at the end of the study). In this case the duration will be presented as “>x days”.

An AE for which the study drug was discontinued is defined as an AE with action taken “drug withdrawn”.

Severity is classed as mild/ moderate/ severe/ life-threatening/ death. If a participant reports a TEAE more than once within that SOC/ PT, the AE with the worst-case severity will be used in the corresponding severity summaries.

Relationship, as indicated by the Investigator, is classed as “not related” or “related”. If a participant reports the same AE more than once within that SOC/ PT, the AE with the worst-case relationship to IMP will be used in the corresponding relationship summaries.

AEs leading to IMP discontinuation will be identified if “Drug withdrawn” is collected by using the “Action taken with Efgartigimod due to adverse event” from the AE page of the eCRF.

AEs leading to IMP interruption will be identified if “Drug interrupted” is collected by using the “Action taken with Efgartigimod due to adverse event” from the AE page of the eCRF.

Adverse event of special interest (AESsI) can be serious or nonserious, related, or unrelated to the IMP or study procedures. Infections are considered AESIs and are defined as events with a PT that falls under the MedDRA SOC ‘*Infections and infestations*’.

Infusion related reactions (IRRs) are defined as all AEs with a MedDRA PT that is listed in either:

Copyright © 2009, 2010, 2012, 2016, 2018, 2019, 2021, 2024 IQVIA. All rights reserved. The contents of this document are confidential and proprietary to IQVIA Holdings Inc. and its subsidiaries. Unauthorized use, disclosure or reproduction is strictly prohibited.

- MedDRA Hypersensitivity SMQ broad selection.
- MedDRA Anaphylactic reaction SMQ broad selection.
- MedDRA Extravasation events (injections, infusions and implants) SMQ broad selection, excluding implants. and occurs within 48 hours of an infusion/injection, or within 2 days if the AE start time is not available. In case of partially missing AE start date, the AE will be considered an IRR, unless the available parts of the AE start date provide evidence it did not occur within 48 hours of an infusion/injection.

Any deaths during the study are recorded on the “Deaths Details” page of the eCRF. A death case is defined as an AE with outcome ‘fatal’. Fatal events will be presented in a summary table presenting overall TEAEs and a data listing along with primary cause of death.

Summary tables will only include TEAEs. However, all AEs reported during the study will be listed. Summary tables by SOC and PT will be sorted alphabetically.

An overview table of AEs will be presented by treatment to show number and percentage of participants with at least one event, the number of events, and the event rate per 100 patient years of follow-up (PYFU) for the following;

- TEAEs
- Serious TEAEs
- Grade ≥ 3 TEAEs
- Fatal TEAEs
- Treatment-related TEAEs according to the Principal Investigator
- Procedures-related TEAEs
- Serious treatment - related TEAEs
- TEAEs leading to IMP discontinuation
- TEAEs leading to IMP interruption
- TEAEs of Special interest
- IRRs

The event rate per 100 PYFU is defined as $100 * \frac{\text{number of events}}{\text{sum of the follow-up time during which an event is considered treatment-emergent of all participants expressed in years (i.e. divided by 365.25)}}$.

Some examples using the efgartigimod cut-off of 60 days:

With ‘the follow-up time during which an event is considered treatment-emergent’ we mean the following:

- If a participant received medication from Sept 1 until Sept 30, then the follow-up time during which events are considered treatment-emergent is from Sept 1 until 60 days after Sept 30. So, the follow-up time is 90 days.
- If a participant received only medication on Sept 1, then the follow-up time for this participant is 61 days.

Copyright © 2009, 2010, 2012, 2016, 2018, 2019, 2021, 2024 IQVIA. All rights reserved. The contents of this document are confidential and proprietary to IQVIA Holdings Inc. and its subsidiaries. Unauthorized use, disclosure or reproduction is strictly prohibited.

If a participant has no meaningful interruptions (ie, no interruptions of more than 60 days), the follow-up time during which an event is considered treatment-emergent is equal to (last dose date – first dose date + 1) + 60.

Example:

- Subject 1 has 2 TEAEs and a treatment duration (last dose date – first dose date +1) of 15 days => follow-up time = 15 + 60.
- Subject 2 has 1 TEAE and a treatment duration of 45 days => follow-up time = 45 + 60.

Then the event rate per 100 PYFU is calculated as: $100 * (2+1) / [(15+60+45+60)/365.25]$.

The actual duration of the event does not play any role in the derivation of event rate.

All AEs, including pretreatment events will be listed.

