10.3.1. Definition of AE

AE Definition

• An AE is any untoward medical occurrence in a clinical study participant, temporally associated with the use of IMP, whether or not considered related to the IMP• NOTE: An AE can therefore be any unfavorable and unintended sign (including an abnormal laboratory finding), symptom, or disease (new or exacerbated) temporally associated with the use of IMP

Events to be Collected as AEs

• Any abnormal laboratory test results (hematology, clinical chemistry, or urinalysis) or other safety assessments (eg, ECG, radiological scans, vital sign measurements), including those that worsen from baseline, considered clinically significant in the medical and scientific judgment of the investigator (ie, not related to progression of underlying disease)• Exacerbation of a chronic or intermittent pre-existing condition including either an increase in frequency and/or intensity of the condition• New condition detected or diagnosed after IMP administration even though it could have been present before the start of the study• Signs, symptoms, or the clinical sequelae of a suspected intervention-intervention interaction• Signs, symptoms, or the clinical sequelae of a suspected overdose of either IMP or a concomitant medication. Overdose per se will not be reported as an AE/SAE unless it is an intentional overdose taken with possible suicidal/self-harming intent. Such overdoses will be reported regardless of sequelae• Lack of efficacy or failure of expected pharmacological action per se will not be reported as an AE or SAE. Such instances will be captured in the efficacy assessments. However, the signs, symptoms, and/or clinical sequelae resulting from lack of efficacy will be reported as AE or SAE if they fulfill the definition of an AE or SAE

Events NOT to be Collected as AEs

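### An adverse event carried over from ARGX-113-2106 that worsens during the extension is missing from every TEAE table if it keeps its parent-study start date, because the SAP has no worsening clause

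*SAP*

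**What the plan says.** Four provisions meet here. The first three are in SAP section 17.1.1.

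- **Carry-over.** "Also, the AEs listed in previous study of ARGX-113-2106 which are “Ongoing” will be included for OLE study".
- **Definition of a TEAE.** The sentence runs over a page break: "Treatment-emergent adverse events (TEAEs) are defined as AEs with onset on or after the first administration of", continued as "IMP up to and including 60 days after the last IMP administration before the event". The deciding variable is then named: "AEs will be considered treatment-emergent based on their start date/time". Change in grade, change in seriousness and action taken with IMP play no part.
- **Content of the tables.** "Summary tables will only include TEAEs. However, all AEs reported during the study will be listed". Section 17.1.1.1 repeats the restriction for the tables by SOC and PT. In the overview table the serious, grade 3 or higher, fatal, related, discontinuation, interruption and special-interest rows are all TEAE rows.
- **Collection.** Protocol section 10.3.1 includes among the events to be collected as AEs: "Exacerbation of a chronic or intermittent pre-existing condition including either an increase in frequency and/or intensity of the condition".

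Neither document says whether worsening of an AE already on record is entered as a new record with its own start date or as an update of the old one.

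**The concern.** Incidence and severity of AEs and AESIs, and incidence of SAEs, are part of the primary endpoint. In a rollover study, an existing event that gets worse on further treatment is one of the signals to look for. It matters particularly for participants from the parent placebo arm, who first receive efgartigimod in the extension; SAP section 7.2 presents results by parent treatment.

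Under a start-date-only rule, an event that began in the parent study and stays on its original record cannot become treatment-emergent, whatever happens to it later. Any such omission lowers the TEAE counts and never raises them. Two sites seeing the same clinical course could also produce different counts, one by opening a new record and the other by updating the old one.

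The rule also departs from the SAP's own approach elsewhere. Section 6.5 judges laboratory, vital-sign and ECG findings against baseline, and one of its examples is a QTcF already in the 450 to 480 ms band that rises above 500 ms. Worsening of an existing abnormality is treatment-emergent there; for AEs there is no such comparison.

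**Working it through.** **Step 1: reproduce the SAP's own windows.** Let S be the AE start day and L the last dose day on or before S. The event is treatment-emergent if S is on or after the first dose and S − L ≤ 60. The schematic in section 17.1.1 has dosing on days 1–40 and 120–160.

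| S | L | S − L | Treatment-emergent |
|---|---|---|---|
| 100 | 40 | 60 | yes |
| 101 | 40 | 61 | no |
| 119 | 40 | 79 | no |
| 120 | 120 | 0 | yes |
| 220 | 160 | 60 | yes |
| 221 | 160 | 61 | no |

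This matches the schematic (not emergent on days 101–119 and after day 220). The follow-up examples in the same section also agree: 30 + 60 = 90 days and 1 + 60 = 61 days. The rule has been read as the SAP intends.

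**Step 2: apply it to a carried-over event.** Assumed case: the AE began 30 days before the first extension dose, dosing is weekly (days 1, 8, …, 99), and on day 100 the event becomes serious or leads to withdrawal of IMP.

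| How the worsening is recorded | S | Result |
|---|---|---|
| Original record updated, parent start date kept | −30 | no extension dose on or before S: not a TEAE |
| New AE record for the exacerbation | 100 | L = 99, S − L = 1: TEAE |

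The clinical course is identical; only the data entry differs. The worst-case severity rule in section 17.1.1 does not help, because it chooses among repeat reports of a TEAE.

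**Step 3: size.** Inputs are about 30 participants (Protocol section 9.5, SAP section 3.2), last weekly dose at week 47 (day 7 × 47 + 1 = 330), and 60 days added for follow-up. The number of affected events is in neither document; 1 to 3 participants is shown only as an illustration.

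- Percentage of participants: 1/30 = 3.3 points, 2/30 = 6.7 points, 3/30 = 10.0 points. This applies only to a participant with no other event in the same row.
- Event rate: if all 30 are treated to week 47, follow-up is 30 × (330 + 60) / 365.25 = 32.0 patient-years. Each omitted event is 100 / 32.0 = 3.1 per 100 patient-years, whether or not the participant has other events.

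**The case against.** The strongest reply is that the protocol already deals with worsening. SAP section 17.1.1 takes its AE collection from Protocol section 10.3, which treats an exacerbated condition as an AE and excludes day-to-day fluctuations only if they do not worsen. On that reading the exacerbation is an AE in its own right; entered with its own onset date, it is a TEAE. Record-entry rules may also sit in the eCRF completion document named in Protocol section 10.1.8, which is not available here. Finally, the SAP says that ongoing events are included, not expressly that they keep their parent start date.

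Much of this stands, and it limits the point. A reader might infer that such events disappear from every primary safety table, or are never counted. The documents do not support either:

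- Laboratory, vital-sign and ECG results are also primary outcomes and do not use the TEAE flag. A rise in laboratory toxicity grade shows in the cross-tabulation against baseline, including the worst-case visit (SAP sections 6.4 and 17.1.2).
- All AEs, including pretreatment ones, are listed, and treatment stops are tabulated by reason in disposition (SAP section 8.1).
- A worsening entered as a new AE is counted. An event with an incomplete or missing start date is treated as emergent unless the known date parts rule it out.

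Nor should an interval be put around the shift as if it were a planned result. SAP section 7.2 specifies number and percentage for event-type safety data and mentions the 90% CI for efficacy. The study tests no hypothesis.

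The reply does not remove the gap. Making an exacerbation collectable does not say that it gets a new start date. Protocol sections 8.4.3 and 10.3.3 speak of following events and submitting updated SAE data, which fits updating the old record equally well. Listings give no rates, and a stop counted in disposition could be missing from the TEAE discontinuation row.

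**Conclusion.** The point holds in conditional form. A carried-over AE that stays on its original record with its parent-study start date is left out of every TEAE summary table, even if during the extension it rises in grade, becomes serious, or leads to interruption or withdrawal of IMP. Whether this happens depends on a data-entry convention that neither document states.

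The direction is known: it can only undercount. The size is not known, because the number of events ongoing at rollover and the number that worsen are not given. Each omitted participant with no other event in the row costs 3.3 percentage points at 30 participants.

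The conclusion assumes that carried-over records keep their start date and that first administration of IMP means the first extension dose. The second is the natural reading, since SAP section 10 specifies study 2211 for medications, but section 17.1.1 does not say it.

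**What to change.** In SAP section 17.1.1, extend the TEAE definition with wording such as:

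> or an AE ongoing at the first OLE dose that, on or after that dose and within the 60-day window, increases in CTCAE grade, becomes serious, or leads to IMP interruption or discontinuation.

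Also state that:

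- onset of such an event is the date of the change;
- it is counted once if the site has already entered the worsening as a new AE;
- first administration of IMP means the first dose in ARGX-113-2211.

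The cost is one SAP sentence with these clarifications, one programming flag, and a date of change for the carried-over AEs affected, presumably few. That date is not among the AE fields listed in section 17.1.1, so where no new record was opened it would have to be obtained from the site.
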